A final report will be sent to sites at the conclusion of the study with a summary of study results.

M. Addendum Version History

Version	Version Date	Summary of Changes & Rationale	Author(s)/Title
1	27 Jul 2018	Initial Release	[name], Sr. Clinical Program Manager
2	01 Dec 2020	
General administrative changes throughout the document:
 
 Added MCS PSR platform base protocol and DT PAS addendum references and clarifications regarding the names of the protocols Added table of contents, updated glossary, expanded abbreviations as appropriate and other minor editorial modifications, clarifications, and reformatting Updated the synopsis to reflect updates to addendum 
Replaced Intermacs V3.0 adverse event terminology throughout the document to Intermacs V5.0 to align with DT PAS Addendum
 
Section C- Updated Table 1 with updated contact information
 
Section E.2 – Included clarification that Apogee cohort approximation is not limited to 100 patients
 
Updated addendum to align with modifications in the MCS PSR platform base protocol and DT PAS addendum including:
 
 Section E.2 – Updated number of sites from 55 to approximately 50, as stated in DT PAS addendum Section E.3 – Update in the anticipated time to achieve full enrollment duration Section F.1. – Included follow-up assessment Section H – Replaced HVAD IFU with “product labeling, which may include but is not limited to the IFU and the product reference manuals” 
Section G.1 – Added clarifications and rewording for clarity and removed section under 2D color velocimetry since it is included in the Apogee Echocardiography Manual, which is a separate document
 
Section J.4 – Added section to describe known or foreseeable factors that may compromise study outcomes to fulfill ISO14155:2020 requirement
 
Section M – New section to include addendum version history
	[name], Clinical Research Specialist

APPENDIX A: VerifyNow Aspirin Assay: Sample Preparation

The VerifyNow Aspirin Test Procedure should be performed according to manufacturer's instructions provided below:

VerifyNow® Aspirin Test Procedure

Principle

Aspirin affects platelet function by irreversibly inhibiting the cyclooxygenase-1 (COX-1) enzyme involved in the conversion of arachidonic acid to thromboxane A2, which ultimately activates the GPIIb/IIIa receptors involved in platelet aggregation. If aspirin has produced the expected anti-platelet effect, such aggregation will not occur. The VerifyNow Aspirin Test incorporates the agonist arachidonic acid to activate platelets. The Aspirin Test is designed to measure platelet function based upon the ability of activated platelets to bind fibrinogen. Fibrinogen-coated microparticles aggregate in whole blood in proportion to the number of unblocked platelet GP IIb/IIIa receptors. Light transmittance increases as activated platelets bind and aggregate fibrinogen-coated beads. The instrument measures this change in optical signal caused by aggregation.

Materials Required

- VerifyNow Instrument with Electronic Quality Control (EQC).
- VerifyNow Aspirin Test Device (reagent device), 10 (PN: 85053-10) or 25 (PN: 85053), individually sealed in foil pouches. Each test device contains lyophilized fibrinogen-coated beads, platelet agonist, peptide, bovine serum albumin, stabilizer, and buffer.
- Store test devices at 2°C to 25°C (36°-77°F) Store at room temperature.
- Greiner Bio-One Vacuette® 2ml blood collection tubes containing 3.2% sodium citrate. Greiner Catalog # 454322 or Nipro catalog #NP-CW0185-1 blood collection tube (1.8ml) containing Sodium Citrate (3.2%).
- Phlebotomy supplies, including needle of 21 gauge or larger.
- Wet Quality Control (VerifyNow Assay WQC), P/N 85047, Box of 6 Diluent Tubes and 6 Pellets. QC materials are stable at room temperature until the expiration date indicated on the tube or pellet container.

Specimen Collection and Specifications

Specimen Type: Whole blood collected from venous or arterial sites must be collected in or immediately transferred to Greiner 2.0 mL partial fill blue top tubes containing 3.2% Sodium Citrate. The tube must be filled to its intended whole blood capacity (indicated by small black line).

- Samples should be collected between 2 and 30 hours after ingestion of aspirin.
- Blood must set a minimum of 30 minutes after collection before test but no longer than 4 hours.

Instructions for Sample Collection Directly Into Vacuum Collection Tubes:

1. Whole blood may be collected from venous or arterial sites using a 21 gauge or larger needle in partial fill 3.2% citrate vacuum collection tube. Blood samples should be obtained from an extremity free of peripheral venous infusions.
2. Perform the phlebotomy and obtain the appropriate volume of blood in the sample tube following a discard tube of at least 2 mL of whole blood. DO NOT DRAW A SAMPLE FOR ANY PLATELET FUNCTION TEST AFTER A TUBE THAT CONTAINS EDTA (PURPLE TOP). Always draw the sample tube(s) for the VerifyNow Test first.
3. Gently invert the citrated tube containing whole blood 5 times immediately after collection to mix the blood with the anticoagulant and prevent clotting.
4. Samples must be kept at room temperature. Do not refrigerate, freeze or centrifuge the samples to be used for the VerifyNow Test.

5. Samples that are difficult to obtain may hemolyze or clot. Samples that are hemolyzed or clotted should be recollected.

Special Instructions if blood is obtained from an indwelling catheter:

1. Whole blood samples that are obtained from an indwelling catheter should be collected after sufficient discard (approximately 5 mL) has been drawn to clear the line.
2. Ensure indwelling catheter is free of clots.
3. When using a syringe, transfer blood to the appropriate blood collection tube **immediately** after collection.
4. Immediately gently invert the citrated tube containing whole blood at least 5 times to mix the blood with the anticoagulant and prevent clotting.
5. Samples must be kept at room temperature. Do not refrigerate, freeze or centrifuge the samples to be used for the VerifyNow Test.
6. Samples that are difficult to obtain may hemolyze or clot. Samples that are hemolyzed or clotted should be recollected.

Sample Stability and Storage: The sample must be incubated at room temperature for 30 minutes prior to testing and can be used up to 4 hours after collection if stored at room temperature (18 to 25 °C). *Do not refrigerate or freeze specimen.*

Sample Precautions: Collection of the blood specimen should be performed with care to avoid hemolysis or contamination by tissue fluids. Samples with evidence of clotting must not be used.

Interfering Substances:

Laboratory testing was performed to determine the effects of several classes of drugs on VerifyNow Aspirin Test results. The following medications may cause a change in platelet function. The following information should be considered for patients who are to be tested with the VerifyNow Aspirin Test.

P2Y12 Inhibitors: Plavix®, Ticlid®, and Effient® are commonly prescribed in conjunction with aspirin. While infrequent, these agents may cause a reduction of ARU in some patients. However, the effect of the P2Y12 inhibitors did not affect the categorization of patients taking aspirin as having platelet dysfunction (i.e. ARU < 550) due to aspirin ingestion. The duration of inhibitory effects varies among these P2Y12 inhibitors. Average durations are listed below:

- Plavix (up to 5 Days)
- Ticlid (up to 5 Days)
- Effient (up to 10 days)

Other Anti-Platelet Agents: These agents can all inhibit platelet function and may result in a decreased ARU value independent of the effects of aspirin. The duration of inhibitory effects varies among drugs. Average duration times are listed for each drug.

- Aggrenox (10 days)
- Persantine (12 hours)
- Pletal/Cilostazol (12 hours)

NSAIDs: Like aspirin (ASA), NSAIDs have been documented to inhibit platelet function. Unlike ASA, NSAIDs do not irreversibly inhibit platelet function. This may lead to less platelet inhibition by ASA if the NSAID and ASA are taken at the same time. Average duration times for these inhibitory effects are given for each drug.

- Ibuprofen (Motrin, Advil) (8 hours)

- Naproxen (Aleve, Anaprox, Naprelan, Naprosyn) (24 hours)
- Diclofenac (Voltaren, Cataflam) (24 hours)
- Indocin (24 hours)
- Feldene (50 hours)

GP IIb/IIIa Inhibitors: Patients who have been administered tirofiban (Aggrastat®) or eptifibatide (Integrilin®) within two days, or abciximab (ReoPro®) within two weeks should not be tested.

Other classes of commonly used drugs were tested with no significant effect on VerifyNow Aspirin Test performance (antioxidants, ACE inhibitors, antiarrhythmics, anticoagulants, antidepressants, insulin, allopurinol, alcohol, beta blockers, bronchodilators, calcium channel blockers, gastrointestinal medications, betamethasone, lovastatin, and the thyroid hormone L-thyroxine). The thrombolytic agent streptokinase showed a measurable inhibition of platelet function, as measured by the VerifyNow Aspirin Test.

Laboratory and clinical testing was performed to assess the effect of the levels of several blood constituents:

Test performance was not affected by hematocrit values between 29-56%, platelet count values of $\geq 92,000$ platelets per microliter or moderate to extensive blood hemolysis induced by physical manipulation. The degree of hemolysis was determined by visual examination of plasma from centrifuged samples collected concurrently with VerifyNow Aspirin Test samples.

No significant interference was observed on samples studied with triglyceride concentrations up to 577 mg/dL.

Fibrinogen levels between 164-529 mg/dL were tested with the VerifyNow Aspirin Test. No known relationship exists between performance of VerifyNow Aspirin Test and fibrinogen levels.

Handling Conditions

The sample must be incubated for 30 minutes at room temperature prior to testing. If testing is delayed, the sample can be stored at room temperature (18 to 25 °C) for up to 4 hours. *Do not refrigerate or freeze specimen.* The sample must be handled in accordance with all policies and procedures relating to the collection, processing and disposal of biohazardous samples.

Reagent Storage and Handling

Reagents Required:

1. All required reagents are contained within the individually packaged VerifyNow Aspirin Test device. Each test device contains lyophilized fibrinogen-coated beads, platelet agonist, peptide, bovine serum albumin, stabilizer, and buffer.
2. Each individually sealed test device contains the lot number and expiration date stamped on the foil pouch.
3. Once removed from its foil pouch, the test device must be handled only by the finger grip and used immediately.

Receipt of Shipment:

1. When a shipment of kits is opened, check the temperature indicator located on the outside of the box. If the temperature indicator is activated, this indicates exposure to elevated temperatures and a VerifyNow Level 2 WQC should be performed.
2. If the Level 2 WQC result does not fall within the accepted range on the package insert, call Accumetrics Technical Support at [contact].

Storage Temperature:

1. Store Test Devices at 2° C to 25° C (36° - 77° F).

2. If refrigerated, allow test devices to reach room temperature, 18° C to 25° C (64° -77° F), prior to use.
3. **Test devices should remain sealed in the foil pouch until ready for use to prevent damage by humidity.**

Reagent Quality Control:

1. The manufacturer recommends that a Level 2 WQC be run once each time a new lot or a new shipment of VerifyNow Aspirin Test kits is received. A Level 2 Quality Control should also be performed on each lot of test devices whenever a problem is suspected with the temperature indicator of a newly received lot of test devices.
2. Level 1 and Level 2 Quality Control must also be performed at the frequency specified. Please refer to the Quality Control section below for additional instructions.

Calibration and Calibration Verification

1. The VerifyNow Aspirin Test devices are calibrated by the manufacturer at the factory. This calibration information is contained in the barcode on the pouch of each test device.
2. The barcode must be scanned whenever a new lot of test devices is to be tested. The system will not allow a test device to proceed without the lot number calibration information entered into the system. If a new lot of test devices is being used, the instrument will prompt the user by displaying a barcode icon after the test device is inserted.
 - a. At prompt, place the test device pouch approximately one inch in front of the barcode reader found on the left side of the instrument, so that the light shines on the center of the barcode.
 - b. An audible beep will be heard when the instrument receives the required information.
 - c. The user needs only to perform this action once per lot.
3. No additional calibration is performed by the user.
4. Calibration verification is performed by the use of WQC materials with every new lot of reagent and at specified time intervals, with periodic review of QC results by the laboratory technical supervisor. Tests of platelet reactivity are non-linear, and no additional calibration verification is required.

Quality Control Procedures

Electronic Quality Control: The Electronic Quality Control Device (EQC) is supplied with each instrument and must be run each day of use prior to reporting patient results. This device verifies instrument optics, reagent mixing and instrument pneumatics. Refer to the VerifyNow System User Manual for additional information.

1. If required, enter Operator ID and Password.
2. The EQC Device is located in a storage port on the right side of the instrument.
3. Choose QC by pressing the QC button from the main screen.
4. Open instrument cover. Remove the EQC Device from the storage port, open instrument cover and insert the EQC Device into the instrument. Close instrument cover.
5. EQC will automatically run.
6. Open instrument cover and remove the EQC Device and return it to the storage port. Close instrument cover. A result of PASS or FAIL will be displayed.
7. If the EQC Device result is "FAIL", repeat the EQC. If the result is "PASS", continue with patient testing. If the EQC result is "FAIL" after the second analysis, use the cleaning cartridge as described in the Maintenance Section below and rerun the EQC.
8. Print result and keep as source document.

Wet Quality Control: The manufacturer recommends that a Level 2 WQC be run once each time a new lot or a new shipment of VerifyNow Aspirin Test kits is received. The Wet Quality Control (WQC) procedure must also be performed whenever a problem is suspected with the temperature indicator of a newly received lot of test devices, whenever a problem is suspected with the VerifyNow System, and as part of the laboratory quality control program.

Sample Preparation:

1. All control material should be stored at room temperature (18 to 30 °C).
2. Do not open the vial containing the Level 2 Control pellet until immediately prior to use.
3. Control Level 1 is ready for use as provided.

Wet Quality Control:

1. If required, enter Operator ID and Password.
2. Press the QC Icon key. The *Insert Cartridge* screen will display.
3. Open the foil pouch and remove the test device. The test device should only be handled by the finger grip.
4. Remove the protective sheath from the test device needle by pulling directly up on the sheath. Do not twist the sheath as this may remove the needle.
5. Open instrument cover. Insert the test device at the instrument prompt. If this is a new device lot, the Bar Code prompt will display. At prompt, place the test device pouch approximately one inch in front of the barcode reader found on the left side of the instrument, so that the light shines on the center of the barcode. An audible beep will signal that the instrument has read the bar code, and the testing will continue.
6. Prepare the WQC Sample.
 - a. Level 1: Test Control Level 1 is ready for use as provided.
 - b. Level 2: Remove the stopper from the tube containing the Level 2 Control diluent by twisting and pulling the cap simultaneously.
 - c. Add the Level 2 control pellet to the Level 2 control diluent tube and replace the stopper by pressing and turning simultaneously.
 - d. Invert the tube gently 5 times to mix.
7. At the prompt, insert the sample onto the device needle. Close instrument cover. The test will automatically begin. **CAUTION:** The sample is under pressure once it is inserted onto the device needle. DO NOT REMOVE the test device or control tube from the instrument until the test is completed.
8. The instrument will run the test and display the result.
9. Print or record the result and return to the Main Screen.
10. Open instrument cover. Remove the test device by grasping the device finger grip and pulling straight up. Do not remove the sample or diluent tube from the device. Close instrument cover.
11. Discard the used device and quality control tube as biohazardous waste.
12. The instrument is ready to test the next sample.
13. Determine that the WQC result is within the acceptable range of values printed on the test device pouch provided with the test.
14. If the WQC is in control, proceed with the test of patient samples. If the WQC is out of range, follow the procedure established by your institution.
15. Print result and keep as source document.

System (Internal) Quality Control for Each Sample Tested:

1. Each time a test device is run on the VerifyNow System, the instrument verifies the test device expiration date, sample filling, optics performance, correct fluid transfer, and proper mixing.
2. The system controls prevent the operator from running an expired test device.
3. The system also detects certain other operator errors, such as placing the test device or the sample in the instrument at the wrong time, or removing the test device before the test is complete. These controls prevent reporting of an inaccurate test result.
4. The test device internal controls in the VerifyNow Aspirin Test device can detect failures of the reagent system due to improper storage or handling conditions.

5. The internal controls will flag an improperly collected or mishandled blood sample, or a blood sample with certain types of interfering substances.
6. The test device internal controls detect errors from the reagent system, adverse environmental conditions, and additional types of operator errors.

RECALL OF EQC OR WQC RESULTS:

1. The last 100 EQC and WQC results can be recalled at any time. You may scroll by using the arrow keys on the keypad.
2. Press the Maintenance button from the Main Screen.
3. Press the Next arrow 3 times to advance to the Maintenance Submenu where folders are displayed with the words EQC (2nd button) and WQC (3rd button).
4. Press the appropriate button to recall the EQC or WQC results.
5. Press the back arrow to return to the Main Screen.

Testing Patient Samples

1. Refer to the VerifyNow System User Manual for complete operating instructions.
2. Power on the instrument. This will initiate the following startup checks:
 - a. A system program and data memory check to ensure memory integrity;
 - b. A system temperature check to ensure the test device warming plate reaches and maintains the proper temperature;
 - c. A system check of proper operating voltages; and
 - d. A system intra-communication validation.
3. Perform Electronic Quality Control if one has not been performed within the required timeframe. The following checks are performed:
 - a. Instrument optics.
 - b. Pneumatics system that draws the sample into the test device and moves it into the test device for reaction and measurement.
 - c. Reagent mixing parameters and sample data acquisition.
 - d. Correct calibration parameters.
4. If required, enter Operator ID and Password.
5. If required, enter the Patient ID.
6. Open the foil pouch and remove the test device. Test devices should only be handled by the finger grip.
7. Remove the needle's protective sheath by pulling directly up on the sheath. Do not twist the sheath as this may remove the needle.
8. Open instrument cover. Insert the test device at the instrument prompt. If this is a new device lot, the Bar Code prompt will display. At prompt, place the test device pouch approximately one inch in front of the barcode reader found on the left side of the instrument, so that the light shines on the center of the barcode. An audible beep will signal that the instrument has read the bar code, and the test will continue.
9. At the instrument prompt, invert the sample tube at least 5 times, and insert onto the needle in the test device. Close instrument cover. CAUTION: Sample is under pressure. Do not remove sample tube from test device. Only remove test device from the instrument after the test is completed.
10. The instrument will run the test and display the result in less than five minutes.
11. Record or print the sample result.
12. Open instrument cover. Remove the test device by grasping the device finger grip and pulling straight up. Do not remove the tube from the test device. Close instrument cover.
13. Dispose of the entire test device/sample tube in appropriate biohazard waste container.
14. The instrument is ready to test the next sample.

Recall Patient Results: In order to enable the recall of specific patient results, the instrument must be configured to require a Patient ID to be entered before each test device is performed.

1. If required, enter Operator ID and Password.
2. CHOOSE THE SECOND OPTION (BUTTON NEXT TO FILE FOLDER) FROM THE MAIN SCREEN.
3. Enter the Patient ID, and press the arrow for Next.
4. An Aspirin Test result is indicated by an "a".
5. Record or print the results. The most recent result is displayed, along with the date stamp indicating the date and time the test was performed. To toggle to other results, use the left and right arrow key.
6. If you choose the PRINT ALL icon, everything displayed below the blinking cursor will print.

Reported Results

Test results are reported as Aspirin Reaction Units (ARU), which are calculated as a function of the rate of aggregation. Interpretation of results is based on the following assigned cutoffs:

Interpretation of Results:

≥550 ARU - Platelet dysfunction consistent with aspirin has not been detected

< 550 ARU - Platelet dysfunction consistent with aspirin has been detected

Results should be interpreted in conjunction with other laboratory and clinical data available to the clinician.

Reference Range:

The reference range for pre-aspirin samples is 620-672 ARU.

Test Limitations and Method Notes

1. To minimize problems during specimen handling, test performance and reporting of test results, the area where testing is performed must contain the proper workbench space, ventilation, utilities, and supplies necessary for conducting the type and volume of testing performed.
2. Place the VerifyNow instrument on a clean, firm, level bench top, which is free of excessive vibration from equipment such as a centrifuge. Provide adequate space around the instrument to access instrument components and be sure the area is free from exposure to unusual temperature fluctuations.
3. Do not locate the VerifyNow instrument in an area next to a source of heat, air conditioning or in direct sunlight. Do not place the instrument under an incandescent light source.
4. The VerifyNow instrument operates at ambient temperature (18-32°C or 64-90°F) and up to 85% humidity without condensation.
5. The lyophilized agent is hygroscopic and can degrade after prolonged exposure to room air. Therefore, the test device should be used shortly after removal from the foil pouch.
6. Store reagents and quality control material according to the package directions. The test devices can be stored either at room temperature or in the refrigerator.
7. Delays in testing or difficulty of specimen collection may result in spurious values. Do not test any sample that is clotted, too old, hemolyzed or that has been mishandled or mislabeled.
8. When results are not within the expected limits, the possibility of improper sample collection or handling should be investigated. Repeat the test using a new test device and sample.

9. Patients with inherited platelet disorders such as von Willebrand Factor Deficiency, Glanzmann Thrombasthenia and Bernard-Soulier Syndrome have not been studied with the VerifyNow Aspirin Test.
10. Patients receiving the following anti-platelet agents may not be tested with VerifyNow Aspirin Test, based on documented interference testing results: GPIIb/IIIa inhibitors, dipyridamole, clopidogrel, non-steroidal anti-inflammatory drugs (NSAIDS) which inhibit COX-1 and/or COX-1, COX-2 enzymes (ibuprofen, naproxen, diclofenac, indomethacin, and piroxicam).
11. The performance of VerifyNow Aspirin Test on patients with acquired non-drug induced platelet abnormalities is not known.
12. The performance of VerifyNow Aspirin Test on patients with acquired non-drug induced platelet abnormalities is not known.
13. Patients who have been treated with Glycoprotein IIb/IIIa inhibitor drugs should not be tested until platelet function has recovered. This time period is approximately 14 days after discontinuation of drug administration for abciximab (ReoPro) and up to 48 hours for eptifibatide (Integrilin) and tirofiban (Aggrastat). The platelet function recovery time varies among individuals and is longer for patients with renal dysfunction.
14. The VerifyNow Aspirin Test results should be interpreted in conjunction with other clinical and laboratory data available to the clinician.

Diagnostic Error Display Messages:

Under certain conditions, a test run may be aborted. In this case, the instrument will display an Error or Attention message. Please refer to the VerifyNow User Manual for a more detailed explanation of these messages.

Maintenance

1. The Maintenance and Setup Icon is used to setup users, change the date and time, recall QC results, network the instrument, set patient ID requirements and for troubleshooting. This function should only be performed by users with proper training and authority. Refer to the User Manual for additional information.
2. Keep the surface of the instrument clean with any commonly used laboratory disinfectant specified in the User Manual. Accumetrics recommends that the exterior surface be cleaned no less than monthly.
3. Cleaning Device: Once every other week, or if the EQC Device fails twice. REMOVE THE TAPE FROM THE CLEANING DEVICE AS INDICATED. Place the device in the test well for 5 seconds and remove. Dispose of the single use cleaning device. Rerun the electronic QC device. If the EQC does not pass, call Accumetrics *Technical Support* at [name].
4. If the EQC device becomes contaminated, wipe with a damp cloth.
5. Replace the fan filter yearly (see Section 10.2 of the User Manual for additional information).
6. Other than fuse replacement, the external power cord, or parts discussed above no other user-serviceable parts exist on the VerifyNow Instrument. Contact Accumetrics *Customer Support* at [name] if further service is required.

References:

1. VerifyNow Assay WQC, Package Insert, P/N 14349
2. VerifyNow Aspirin Test, Package Insert, P/N 14314
3. VerifyNow System User Manual, P/N 14340

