- Diary: Patient to record Doppler pressure, presence of palpable pulse or dizziness, and HVAD measurements from controller (i.e. power, flow, RPM, peak, trough) in diary and bring to site during scheduled visits. Site will record these onto CRF.

Patient should call site if:

- BP >90 for 3 consecutive days or if postural symptoms >48 hours (e.g. orthostatic reaction)
- BP >110 for single timepoint (take BP measurement twice before calling to confirm both show >110 at timepoint)
- BP <60 for single timepoint (take BP measurement twice before calling to confirm both show <60 at timepoint)
- Patients with symptoms of hypotension (dizziness/syncope/presyncope/weakness) should be instructed to call even if values read normal.

Medication guidelines for hypertensive patients post discharge

- See algorithm

I. Anti-Coagulation / Platelet Therapy Investigation

I.1. Aspirin Management Plan

The site will be asked to report the patient's aspirin dose and dose start date at discharge and throughout follow-up or when the patient presents with a bleeding or thrombotic event, including hemorrhagic or ischemic strokes. Per the HeartWare HVAD System Instructions for Use, "In general, aspirin should be started at doses >81 mg/day" (i.e., moderate-dose aspirin of 162mg or high-dose of 325mg, etc.). The Medication Log captures aspirin dose and any changes.

I.2. VerifyNow Aspirin Assay Laboratory Test

A VerifyNow Aspirin Assay and CBC (if available) will be collected along with the current aspirin dose and its start date at each scheduled follow-up visit through 12 months. The assay and CBC (if available) will also be collected at all Unscheduled Visits, if the patient presents with a bleeding or thrombotic complication, including hemorrhagic or ischemic strokes. See Appendix A for instructions on the use of the VerifyNow Aspirin assay, which is also available online at <http://www.accumetrics.com/products/verifynow-system-platelet-reactivity-test>.

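### Protocol section I.2 requires the aspirin assay at every scheduled visit without a co-medication exception, Appendix A item 10 bars it on several agents, and Appendix A conflicts with itself on clopidogrel, so the descriptive ARU–event correlation could be distorted

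*Protocol*

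**What the plan says.** Protocol section I.2 calls for the VerifyNow Aspirin Assay "at each scheduled follow-up visit through 12 months", and also at unscheduled visits for a bleeding or thrombotic complication. It names no co-medication under which the assay is omitted, and it refers sites to Appendix A for instructions on use. The stated purpose is to relate assay results to bleeding and thrombotic events. That includes asking whether platelet activity differs with the frequency and severity of thrombotic events.

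Appendix A addresses co-medication in two places.

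- **Interfering Substances.** On P2Y12 inhibitors it says that "Plavix®, Ticlid®, and Effient® are commonly prescribed in conjunction with aspirin", that they may infrequently lower the ARU, but that "the effect of the P2Y12 inhibitors did not affect the categorization of patients taking aspirin as having platelet dysfunction", meaning an ARU below 550. On the other anti-platelet agents (Aggrenox, Persantine, Pletal) it says: "These agents can all inhibit platelet function and may result in a decreased ARU value independent of the effects of aspirin". On NSAIDs it says: "Like aspirin (ASA), NSAIDs have been documented to inhibit platelet function". It gives durations of effect for all these groups. The only class it says should not be tested is the GP IIb/IIIa inhibitors, within stated time windows.
- **Test Limitations and Method Notes, item 10.** "Patients receiving the following anti-platelet agents may not be tested with VerifyNow Aspirin Test". The list runs "GPIIb/IIIa inhibitors, dipyridamole, clopidogrel, non-steroidal anti-inflammatory drugs (NSAIDS" and goes on to name five NSAIDs. The reason given is interference testing.

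SAP 7.4 does not impute missing data, and SAP 7.3 pools centres without a poolability assessment. The visible text has no rule for ARU results, or missing assays, in patients on these agents. The ancillary-objective sections of both documents are redacted.

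**The concern.** For a patient on clopidogrel, a site that follows section I.2 draws the sample and departs from item 10. A site that follows item 10 leaves a gap that section I.2 does not foresee. Neither route is neutral for the stated purpose. If the patient is not tested, that patient drops out of the ARU–event comparison, and patients on a second antiplatelet agent may differ in thrombotic or bleeding risk. If the patient is tested, the ARU may reflect the second agent as well as aspirin. With no imputation and with centres pooled, neither effect would show in the output unless someone looked for it.

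**Working it through.** The documents give no figure on this point, so there is none to reproduce. The check compares texts, followed by a rough scale.

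**Texts side by side**

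| Agent | Section I.2 | Appendix A, Interfering Substances | Appendix A, item 10 | Relation |
|---|---|---|---|---|
| Clopidogrel (Plavix) | Test; no exception | Category unaffected; ARU may fall infrequently | May not be tested | Appendix A conflicts with itself; item 10 conflicts with I.2 |
| Ticlid, Effient | Test; no exception | Same statement as Plavix | Not listed | No conflict |
| Dipyridamole products | Test; no exception | Interference warned of, with durations; no bar | May not be tested | Warning against bar; item 10 conflicts with I.2 |
| Five named NSAIDs | Test; no exception | Interference warned of, with durations; no bar | May not be tested | Warning against bar; item 10 conflicts with I.2 |
| GP IIb/IIIa inhibitors | Test; no exception | Not to be tested within time windows | May not be tested | Appendix A broadly consistent (item 13 repeats the windows); item 10 conflicts with I.2 |

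So the contradiction inside Appendix A is direct for clopidogrel only. The mismatch between section I.2 and item 10 covers every agent that item 10 lists.

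**Scale**

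Inputs: 124 co-enrolled patients at 34 co-activated sites (SAP 5.2); four scheduled follow-up visits at 1, 3, 6 and 12 months (Protocol F.1). Two further quantities are not in the documents and are assumed: *s*, the share of patients on a listed agent, and *w*, the share of those patients at sites that withhold the test.

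Patients not assayed = 124 × *s* × *w*:

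| *s* | *w* = 0 | *w* = 0.5 | *w* = 1 |
|---|---|---|---|
| 5% | 0 | 3.1 | 6.2 |
| 10% | 0 | 6.2 | 12.4 |
| 20% | 0 | 12.4 | 24.8 |
| 30% | 0 | 18.6 | 37.2 |

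The *w* = 1 column is also the number of patients under conflicting instructions, whatever sites actually do. In samples, the ceiling is 124 × 4 = 496. At *s* = 10% that gives 496 × 0.10 = 49.6, and at 20% it gives 99.2. These are upper bounds: they assume that every co-enrolled patient is implanted and attends all four visits, and that use of the agent is constant.

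**What selection could do**

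Suppose event risk is *r* off the agents and *k* × *r* on them, and no exposed patient is tested. Cohort risk is (1 − *s*)*r* + *s k r*, and risk among tested patients is *r*. The understatement is therefore *s* × *r* × (*k* − 1). With *r* = 0.30 (assumed):

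- *k* = 1: zero at any *s*.
- *k* = 2: 0.05 × 0.30 × 1 = 1.5 points at *s* = 5%; 3 points at 10%; 6 points at 20%; 9 points at 30%.

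This shows only that the tested group can differ from the cohort. It does not estimate the bias in the ARU–event correlation, which would need data that the documents do not contain.

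**The case against.** The strongest reply has five parts.

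1. *The conflict is narrow.* The P2Y12 statement does not extend to dipyridamole or NSAIDs. For those, the two parts of Appendix A point the same way and differ in strictness. Ticlid and Effient are not in item 10. This stands, and it limits the internal contradiction to clopidogrel.
2. *Section I.2 refers to Appendix A, so item 10 can be read as its exception.* This is a fair reading, but section I.2 does not say so. A site would still find the clopidogrel statement under Interfering Substances pointing the other way. Reading item 10 as merely permissive is weak, because its list includes GP IIb/IIIa inhibitors, which Appendix A says elsewhere should not be tested.
3. *Selective loss is not shown.* A reader might infer that assay missingness will be site-dependent and selective. The documents do not support that. If all sites follow item 10, missingness follows drug use and not site. If all follow section I.2, this cause produces none, though some ARU values may be affected. Selection bias also requires exposed patients to differ in event risk or platelet reactivity, which is plausible but not shown.
4. *The stakes are low and partly anticipated.* The assay does not enter the primary Kaplan-Meier endpoint, no hypothesis is tested, and the objectives are hypothesis-generating. Protocol section J and SAP 7.9 expect variation in data collection, and SAP 7.9 promises completion metrics where data are too few. All of this stands. Completion metrics alone would not separate samples by co-medication, however.
5. *A handling rule may sit in the redacted ancillary sections.* This cannot be excluded, so the analysis half of the fix is conditional. The conflicting site instructions are in visible text and do not depend on it.

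**Conclusion.** The point holds in this limited form. Section I.2 and Appendix A item 10 give incompatible instructions for every agent in item 10, and Appendix A conflicts with itself for clopidogrel. As a result, ARU data could be selectively missing, or could mix co-medication effects with the aspirin effect, in the descriptive correlation with bleeding and thrombotic events. The primary endpoint is not affected.

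The size is unknown. About 6 to 37 of 124 patients would be under conflicting instructions if 5% to 30% took a listed agent, and that range is an assumption. The number actually left untested could be zero. The point is worth correcting because the correction is cheap and protects the stated use of the assay. The documents do not establish that any bias occurred.

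**What to change.** **Instructions.** The sponsor should reconcile section I.2, the Interfering Substances text and item 10 into one testing rule. This review does not say which rule is right. Implants have ceased and all patients were enrolled when the SAP was written (SAP section 3), so a site clarification may reach few remaining samples. The analysis step is then the more useful part.

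**Analysis**, unless the redacted ancillary sections already provide for it:

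- Flag each ARU sample taken while an agent listed in item 10 is recorded in the medication data. SAP Table 1 says that medications are collected through the entire registry.
- Summarise ARU, and its relation to events, both with and without the flagged samples. Showing both matters: excluding them imposes the same selective loss on the whole cohort, and including them leaves interference in.
- Report missing assays by co-medication and by site, which shows directly whether the conflict made a difference.

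**Cost.** Slightly more analysis work and fewer samples in the restricted summary. Timing may be incomplete: Protocol section I.1 says that the Medication Log captures aspirin dose and changes, but last-dose dates for other agents are not shown to be collected. The flag may therefore have to rest on recorded use at the visit, without time since last dose.
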